13. SAFETY MONITORING AND ADVISORY COUNCIL

This study will maintain scientific independence and will be governed by an independent Safety Monitoring and Advisory Council (SMAC). Bayer Schering Pharma AG Berlin will provide an unconditional grant. The Berlin Center for Epidemiology and Health Research (ZEG), Germany and its research team will be accountable to SMAC in all scientific matters.

The SMAC members will be international experts in relevant scientific fields (e.g., epidemiology, gynecology, cardiology and oncology). The members will receive remuneration of expenses and an honorarium to compensate for loss of potential earnings during their work for SMAC. The members will not be involved in or paid for the operational conduct of the study.

14. STUDY MANAGEMENT

This study will be conducted in accordance with

- 'Guidelines for Good Pharmacoepidemiology Practices (GPP)' issued by the International Society for Pharmacoepidemiology in 2007
- 'Good Epidemiological Practice (GEP) – Proper Conduct in Epidemiologic Research' issued by the International Epidemiological Association (IEA) European Federation in 2007
- The ethical principles that have their origin in the Declaration of Helsinki.

15. ETHICS AND PRIVACY

The study will only start after all relevant legal, administrative and ethical requirements (including all requirements regarding the enrollment of minors) have been fulfilled. Information on the identity of the patients and treating physicians will be kept separated from the clinical information throughout the study. All relevant national data protection laws will be followed. The study protocol will be submitted to the relevant Ethics Committees, Institutional Review Boards and regulatory authorities for comments and approval.

Subjects will sign informed consent forms at baseline after reading a subject information sheet and discussing the study with the participating physician. The physician will describe the purpose of the study, the non-interventional character of the study, timing and expected content of follow-up phase contacts, and collection of alternative contact information. Consent will include permission to contact any treating physician to follow up on specific safety outcomes. Subjects will be informed that ZEG's study team will contact them during the follow-up phase to ask a predefined set of safety related questions or to update alternative contact information. Answers to these questions will remain anonymous when forwarded to Bayer Schering Pharma AG or the Safety Monitoring and Advisory Council.

Subjects will be asked to provide personal contact information (e.g., telephone number, home and e-mail address) and information regarding alternative contacts (e.g., relative, friend, general practitioner) in case they cannot be reached. In the event that a subject cannot be reached during the follow-up phase, local organizations will attempt to reach an alternative contact to re-establish contact with the subject. Subjects may be contacted between two follow-up points to confirm that their personal contact information is correct.

Subjects retain the right to withdraw their consent at any time during the study.

16. STUDY FEASIBILITY

ZEG has performed large, multi-national (including transatlantic), observational studies on pharmacoepidemiological issues for the past 20 years – in particular in the area of women's health care. Many of these studies have prospectively followed-up patients for 5-10 years. In addition ZEG has played a pivotal role in developing the EURAS/INAS study design. ZEG has established a broad network of several thousands gynecologists and OC prescribing physicians in the US and Europe who are currently recruiting women for INAS-like studies. With this established international network no major problems are expected for the recruitment of study participants. Furthermore, the drop-out and follow-up rates presented in this study protocol are based on comprehensive experience from similar studies. Therefore the conduct of the INAS–FOCUS study according to this study protocol has a high probability of success.

17. MILESTONES

Precise recruitment and follow-up milestones will depend on the specific launch dates of folate-fortified OCs in Europe and the USA. However, we anticipate the first patient to be recruited in November 2010 in the USA and 2011 in Europe. The first Safety and Medical Advisory Council (SMAC) will take place in the second quarter of 2011, and 6-monthly during Part I of the study. Unless otherwise agreed upon by SMAC members, SMAC meetings will take place annually during the 2nd evaluation phase (years 6 – 15). Written reports up-dating regulatory authorities of the study progress and important SMAC decisions will follow these meetings. The evaluation and analysis of cardiovascular end-points (VTE, ATE) and a first interim analysis of colorectal cancer will take place 5 years after the recruitment of the first study participant. After 15 years of follow-up, the study will end and final evaluation and analysis of colorectal and other cancer end-points will take place. A comprehensive study report will be made available at the completion of the 5, 10 and 15-year evaluation.

APPENDIX 1: VALIDATION OF SELF-REPORTED EVENTS

- **Definite Event:**

Confirmed by diagnostic measures with high specificity (e.g., phlebography for DVT, spiral CT for pulmonary embolism, cerebral MRT for cerebrovascular accidents, ECG with typical ST segment elevation for acute myocardial infarction, histology for cancers, two-sided blood pressure measurement with diastolic blood pressure of more than 120 mmHG for hypertensive crisis)
- **Probable Event:**

Absence of confirmation by a diagnostic measure with high specificity, but clinical diagnosis confirmed by a health professional or supported by diagnostic tests with low specificity (such as D-dimer for VTE, typical ECG/blood gas tests for PE or confirmation of diagnosis by the treating physician for colorectal cancer). These cases are usually characterized by a subsequent specific therapy (such as fibrinolysis, long-term anticoagulant therapy or chemotherapy/radiotherapy). However, if the attending physician confirms that the diagnosis is correct, the event will be classified as a probable event even if specific treatment was not given.
- **Event not confirmed:**
 - Diagnosis reported by the patient is excluded by diagnostic procedures
 - A different medical condition is diagnosed by the attending physician
 - The woman did not contact a health professional to clarify her symptoms and no diagnostic measures were performed that could have clarified the diagnosis

Definite and probable events will be classified as 'confirmed events'.

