1. INTRODUCTION

In the forthcoming months new oral contraceptives (OCs) containing drospirenone (DRSP) or dienogest (DNG) as well as ethinylestradiol (EE), and metafolin (INN: levomefolate calcium) will be introduced. Oral contraceptives are an effective and popular method of birth control, with the majority of women in Europe and the US using OCs at least once in their lifetime. Over the past 50 years their safety has been improved with reductions in the estrogen and progesterone dose. Overall, the risk/benefit ratio is positive for the majority of women who need reversible and reliable contraception. However, special attention regarding oral contraceptive safety amongst women with risk factors for venous and arterial thromboembolism, as well as cancer, is necessary.

OCs containing DRSP - a progestogen that is also an aldosterone antagonist - have been available since the early 2000s. Results from the EURAS-OC [1] and the Ingenix study [2] showed that for all clinical outcomes studied - and in particular cardiovascular outcomes - there was no increased risk for users of DRSP/EE compared to users of other OCs (including OCs containing levonorgestrel (LNG)). The study results were robust enough to show non-inferiority of DRSP/EE regarding the cardiovascular outcomes of interest. In contrast, two recently published studies [3, 4] suggested that the risk of venous thromboembolism (VTE) might be slightly higher for DRSP/EE compared to LNG/EE. However, these two studies had several methodological shortcomings that resulted in an overestimation of the DRSP cohort risk [5]. Overall, the scientific discussion concerning the impact of bias and confounding on the estimates for the VTE risk associated with OC use has not been fully resolved [1-18]. The most parsimonious interpretation of the evidence that exists to date suggests that the VTE risk associated with the use of DRSP/EE and LNG/EE are similar. The addition of folate to progestogen/estrogen combinations has probably no impact on the risk of VTE. However, robust clinical data is not available and therefore an investigation of the VTE risk associated with the combination of DRSP, EE and folate is required.

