8. VALIDATION OF SELF-REPORTED EVENTS

A self-administered questionnaire used by study participants is a very sensitive tool which captures almost all serious clinical outcomes. From a methodological point of view, it captures a much higher proportion of these outcomes than methods relying only on the prescribing gynecologist who often is not involved in the diagnosis and treatment of these outcomes. However, it must be considered that there is a significant difference between the rates of reported and validated events, because laypersons often misclassify adverse events. Therefore, validation of the self-reported events is of utmost importance.

Validation of self-reported events begins at the level of the national field organization with a review of all subjective "events." Potential serious outcomes are reported to ZEG on a daily basis and validated by ZEG.

If an event is reported by a participant, the subjectively perceived symptoms, signs of a disease and if possible the diagnosis as understood by the patient has to be recorded. The name and address of the relevant physician (attending physician, physician responsible for the follow-up treatment after discharge from hospital, or primary care physician) should be provided by the participant.

Follow-up questionnaires containing information on such an event are to be immediately passed on to the medical reviewer group at ZEG. If information is unclear or missing the woman will be contacted by phone, e-mail or other means. For many serious outcomes it will be necessary to contact the diagnosing and/or treating physician for clarification and validation of the information received from the patient. This procedure is mandatory for all serious clinical outcomes (incl. VTE, ATE and cancer).

Under routine medical conditions, diagnosis of an SAE is not always confirmed by a diagnostic method with high specificity. Therefore, SAEs are classified by the investigators as "confirmed" or "not confirmed" according to a predefined algorithm (cf. Appendix 1).

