In order to minimize classification bias - particularly if selectively affecting an individual exposure cohort - classification of self-reported serious events into confirmed and not confirmed cases will be adjudicated by two blinded medical boards. The 'Cardiovascular Board' consists of three independent medical experts specialized in radiology/nuclear medicine, cardiology, and internal medicine/phlebology. The meetings of this board should take place 5 years after study start. The 'Colorectal Cancer Board' consists of an oncologist specialized in colorectal cancer, a pathologist and a radiologist. Blinded adjudication of CRC are scheduled for 5 years after study start and at the end of the follow-up phase (15 years after study start). The Safety Monitoring and Advisory Council (see section 13) will appoint these experts who will review all available information on the reported VTE/ATE/CRC.

However, brand names, dose, regimen and composition of the OC(s) used by the reporting woman will be rendered anonymous. The adjudicators will perform the review independently of each other and without knowing the judgement of the other adjudicators. If at least one adjudicator classifies a report as confirmed VTE or colorectal cancer, the reported event will be considered 'confirmed'. More details on the blinded adjudication procedure are given in Appendix 2.

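### A VTE can be confirmed on a physician's word and is pooled with imaging-proven VTE; no text asks the blinded board for objective evidence, so definite events should be recorded and analysed separately

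*Protocol*

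**What the plan says.** **Confirmation rule (protocol, Appendix 1).** A definite event needs a diagnostic measure of high specificity. A probable event lacks one but has a "clinical diagnosis confirmed by a health professional or supported by diagnostic tests with low specificity". Specific treatment is usual but not needed: "if the attending physician confirms that the diagnosis is correct, the event will be classified as a probable event". The two classes are then merged: "Definite and probable events will be classified as" confirmed events. Section 3 accepts that VTE is not always imaged in routine care, so the probable class will be used.

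**Adjudication (protocol, sections 3 and 8, Appendix 2).** Section 8 has the investigators apply Appendix 1. Section 3 says blinded independent adjudication then verifies that classification. Section 8 gives the aim: "In order to minimize classification bias - particularly if selectively affecting an individual exposure cohort". The cardiovascular board of three specialists reviews all available information, and "brand names, dose, regimen and composition of the OC(s) used by the reporting woman will be rendered anonymous". The board's outcome is confirmed or not confirmed. The final analysis uses strategy III, in which one adjudicator's vote before any discussion is enough. Appendix 2 calls this the most conservative approach. Alternative analyses are possible on request.

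**Primary test (protocol, sections 11 and 12).** Non-inferiority of DRSP/EE+ to established OCs on the VTE hazard ratio, limit 2, one-sided 0.025.

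**The concern.** Masking the adjudicators deals with their own judgement. It does not reach a judgement already in the file. When a VTE rests on clinical opinion alone, the main evidence before the board is the opinion of a physician who was not masked. In a non-interventional study that physician may well have known which pill the woman took. Section 1 reports two studies that "suggested that the risk of venous thromboembolism (VTE) might be slightly higher for DRSP/EE compared to LNG/EE", so a physician's readiness to make a clinical-only diagnosis could differ by product.

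A second route needs no difference between cohorts. False positives that arise at the same rate in both cohorts pull a hazard ratio above 1 towards 1. In a superiority trial that costs power. In a non-inferiority trial it makes the claim easier to reach.

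At stake is the reading of the primary result. With the two classes pooled, a reader cannot tell whether an upper limit above or below 2 rests on proven thrombosis or on clinical labels.

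**Working it through.** **Inputs from the protocol.** Exposure at five years about 185,000 women-years (WY) and VTE incidence 9/10,000 WY (section 12); share of an individual product 7-12% (section 12); one-sided alpha 0.025 (Table 3); limit HR = 2 (section 11).

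**Reproducing Table 3.** With p = margin = 0.0009 and k = share/(1 − share):

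n_ref = (1.960 + 1.282)² × p(1 − p) × (1 + 1/k) / margin²

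- 7% share: 1 + 1/k = 14.286, n_ref = 166,635
- 12% share: 1 + 1/k = 8.333, n_ref = 97,204

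Both match Table 3, so no stated number is wrong.

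**Chance of showing HR < 2 at 185,000 WY.** On the log hazard ratio scale used by the primary hypothesis:

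P = Φ[(ln 2 − ln HR_obs)/SE − 1.96], SE = √(1/e_test + 1/e_ref)

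Baseline events:

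- 7%: e_test = 12,950 × 0.0009 = 11.7; e_ref = 172,050 × 0.0009 = 154.8
- 12%: e_test = 22,200 × 0.0009 = 20.0; e_ref = 162,800 × 0.0009 = 146.5

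e_test is multiplied by HR_obs. The baseline of 63% or 83% is below Table 3's 90% because Table 3 tests a rate difference. That is a separate matter; only the changes count here.

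**Misclassification model (assumptions).** HR_obs = (1 − f) × HR_true + f × g, where f is the false-positive share of confirmed reference VTE and g is the ratio of false-positive rates, DRSP/EE+ to reference. The protocol gives neither.

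| Scenario | HR_true | HR_obs | P, 7% share | P, 12% share |
|---|---|---|---|---|
| No excess | 1 | 1.00 | 63% | 83% |
| f = 20%, g = 2 | 1 | 1.20 | 45% | 64% |
| f = 30%, g = 2 | 1 | 1.30 | 36% | 53% |
| No false positives | 2 | 2.00 | 2.5% | 2.5% |
| f = 20%, g = 1 | 2 | 1.80 | 6.6% | 8.2% |
| f = 20%, g = 0.5 | 2 | 1.70 | 10% | 13% |

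Worked row 2 at 7%: e_test = 14.0, SE = 0.279, (0.693 − 0.182)/0.279 − 1.96 = −0.13, Φ = 45%. Worked row 5 at 7%: e_test = 21.0, SE = 0.233, 0.105/0.233 − 1.96 = −1.51, Φ = 6.6%.

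A 20% excess is small in absolute terms: 0.20 × 11.7 = 2.3 events at a 7% share, or 0.20 × 20.0 = 4.0 at 12%.

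**Precision of a definite-only analysis.** The definite share s is not given. SE grows by 1/√s, so at a true HR of 1:

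- s = 80%: SE 0.340 / 0.267, P = 53% / 74% (7% / 12% share)
- s = 50%: SE 0.430 / 0.337, P = 36% / 54%

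By the more generous Table 3 method the corresponding powers at 185,000 WY are 84% / 96% and 64% / 84%.

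**The case against.** The strongest reply is that Appendix 1 is the investigators' step, while the final analysis rests on a masked board that includes radiology and phlebology expertise and sees all source information. It may reject a diagnosis with nothing behind it. This stands, and it rules out a stronger reading that a reader might infer: that the physician's word settles the primary endpoint and blinding is therefore useless. The documents do not say that, and section 8 promises to minimise bias, not to remove it. But nothing tells the board to ask for objective evidence. Appendix 1 is the only definition of confirmed in the protocol, adjudication verifies that classification, and one vote of three keeps the event.

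Second, the mechanism is inferred. The protocol does not say that the attending physician knows the pill. Section 8 notes that the prescriber is often not the one who diagnoses. Section 1 also criticises the two studies it cites and judges the risks similar. No text shows that diagnosis differs by cohort. All of this stands; the concern is a possibility the design leaves open, not a demonstrated bias.

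Third, a definite-only analysis may be in the statistical analysis plan, which is not shown. Its absence from the protocol is therefore not the finding. What the protocol itself fixes is the confirmation rule, the pooling, the one-vote rule and the claim that this is most conservative. A definite-only analysis on masked judgement also needs a field that the described adjudication does not record.

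Fourth, over-diagnosis under DRSP/EE+ works against the non-inferiority claim, which is the cautious direction. True, but under-diagnosis, or false positives unrelated to cohort, works for it.

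**Conclusion.** The concern holds in a limited form. The protocol lets clinical-only VTE count equally with proven VTE, sets no evidence standard for the board, and keeps an event on one vote. Masking the board reduces its own bias but cannot correct an upstream diagnosis by an unmasked physician.

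The false-positive shares and their ratio between cohorts are assumptions, so the table shows sensitivity and not an expected bias. A reader might infer that the primary hazard ratio is biased against DRSP/EE+; the documents support neither a direction nor a size. What the arithmetic does show is that a handful of events matters, and that equal false-positive rates in both cohorts can roughly triple the one-sided error. A worst-case counting rule is thus not clearly the most conservative choice for a non-inferiority test on a ratio. This is worth changing because the remedy is cheap and leaves the primary endpoint intact; confidence is moderate.

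**What to change.** 1. Keep the pooled definition and strategy III for the primary analysis.
2. State whether adjudicators apply Appendix 1 as written or need objective evidence to confirm a VTE.
3. Have each blinded adjudicator record definite or probable for every VTE that he or she confirms, with a stated rule for combining differing grades.
4. Pre-specify the VTE hazard ratio on definite events as a companion to the primary test, and report the probable share of confirmed VTE by cohort.
5. Commit to saying so in the conclusion if the two analyses fall on different sides of the limit of 2.
6. Drop or qualify the most-conservative label in Appendix 2.

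The cost is one field on the adjudication form, one further Cox model and a few sentences of text. The definite-only analysis has fewer events and a wider interval, most of all at a 7% share, so it should be read as a check on the primary result and not as a second test that must succeed. The field should be in place before the board meets, since grading the same cases again later is much harder.

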APPENDIX 2: BLINDED ADJUDICATION

The following adjudication procedure will be established:

- 1) Independent adjudication by the individual specialists
- 2) Documentation of the individual assessments
- 3) Comparison of the individual assessments
- 4) Discussion of “split decisions” among the adjudicators without enforcement of a unanimous decision
- 5) Independent re-adjudication of the discussed cases by the individual adjudicators
- 6) Documentation of the individual assessments

Based on this procedure four different classification strategies will be possible

- I. Classification of the reported event according to the assessment of the majority of adjudicators before the discussion of “split decisions” takes place (i.e., “majority vote” based on step 2 of the six-step procedure described above)
- II. Classification of the reported event according to the assessment of the majority of adjudicators after discussion of “split decisions” takes place (i.e., majority classification based on step 6 of the six step procedure described above)
- III. Classification of the reported event as confirmed if at least one adjudicator had classified the event as confirmed before the discussion of split decisions took place (i.e., “worst case decision” based on step 2 of the six-step procedure described above)
- IV. Classification of the reported event as confirmed if at least one adjudicator had classified the event as confirmed after the discussion of split decisions took place (i.e., “worst case decision” based on step 6 of the six-step procedure described above)

The final analysis will be based on strategy III (worst case decision without discussion of split decisions) because it represents the most conservative approach. Alternative analyses will be possible on request of the Safety Monitoring and Advisory Council or regulatory authorities.

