11. DATA ANALYSES

The primary variable for inferential statistics is VTE. Based on available data and pharmacological/pharmacokinetic considerations the *a priori* assumption is that use of DRSP/EE+ is not associated with an increased risk of VTE compared to established OCs. That is, a statistical comparison of DRSP/EE+ and established OCs is not expected to show a difference. Therefore, a non-inferiority design to investigate the VTE risk of DRSP/EE+ was chosen. The primary analysis will be based on the comparison of the upper confidence limit for the point estimate of the VTE hazard ratio with the predefined non-inferiority limit (cf. section 12).

The null hypothesis to be tested is: $HR_{VTE} \geq 2$ (i.e., the VTE hazard ratio for DRSP/EE+ vs. established OCs is higher or equal to 2). The alternative hypothesis is: $HR_{VTE} < 2$.

Sub-analyses will include COC+, DNG/EE+, specific regimens of DRSP/EE+ (e.g., the 24-day regimen of 3mg DRSP/20µg EE) as well as starters and recurrent user with and without pill-intake break.

Safety monitoring during study conduct will be based primarily on the ITT analysis of crude data. The final analyses will include both an “as treated” (AT) and an intention-to-treat (ITT) analysis using Cox regression models. The safety conclusions of the study, however, will be based on the AT analyses because the ITT approach potentially dilutes differences between treatments.

Crude as well as adjusted hazard ratios will be calculated. The appropriate confounding variables will be built into the statistical model. Based on the expectation of a small absolute number of serious outcomes of interest the number of confounding variables will be limited to well established risk factors for these outcomes. For VTE/ATE these will include age, BMI, duration of current use, and VTE history. For Colorectal cancer age, BMI, alcohol intake and family history of CRC are planned. The final decision on the confounding variables will be made by the Safety Monitoring and Advisory Council before the first interim analysis of follow-

up data. In addition, alternative analysis will be performed with other potential baseline risks to check the appropriateness of this decision. Similar analyses will be performed for arterial thromboembolism (e.g., acute myocardial infarction and stroke), colorectal cancer and other serious adverse events.

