The study was designed to analyze rare and very rare events (according to the CIOMS classification 1 – 10 and less than 1 event(s) per 10,000 women-years, respectively). The adverse events of particular interest for the sample size calculation are VTE, ATE and colorectal cancer. Based on the EURAS-OC results (see section 1) the estimated VTE and ATE incidence rates in the young study population are ~9/10,000WY for VTE and ~2/10,000WY for ATE. However, in the DRSP/EE cohort, a reduced incidence for ATE (<1/10,000WY) was observed. Since the EURAS-OC results are the most reliable and comparable data available, further calculations are based on these results. For colorectal cancer the expected incidence is 0.65/10,000WY based on the CancerMPact database, which is the best source to derive incidence rates for colorectal cancer in certain sub-populations. Based on this incidence, the following sample size was calculated; in case the study shows other

incidence rates at a later point in time, a re-calculation might be necessary and has to be discussed with the Safety Monitoring and Advisory Council.

The COC+ cohort consists of several newly marketed products and for this combined cohort a proportion of 25-35% of the total study population seems to be realistic. Furthermore it is assumed that the proportion for the individual products will be in the range of 7-12%. Power calculations based on the incidences given above showed that approximately 110,000 to 180,000WY would be needed to show non-inferiority of individual COC+ products versus established OCs for VTE. The calculations for VTE are based on the assumptions given in Table 3. In essence, the study is powered to exclude a twofold risk of VTE for the DRSP/EE+ cohort (primary variable) as well as for folate-containing products with at least 7% of the total exposure – if the true risk of VTE is not different for the individual (sub)-cohorts.

Table 3: Power calculation³² for VTE based on the assumption that the true incidence in the relevant COC+ (sub)-cohort is not different from the reference cohort.

Test significance level, α (one-sided)	0.025 (= 0.05 two-sided)	
VTE Incidence for reference cohort	9/10,000 WY	
Non-inferiority margin	9/10,000 WY (equal to the VTE incidence for the reference cohort)	
Expected VTE incidence for COC+ cohort	9/10,000 WY	
Power (%)	90	
Proportion of COC+ users (% of study population)	7	12
Required women years in COC+ cohort	12,543	13,256

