Required women years in reference cohort	166,635	97,204
Total women years	179,178	110,460

Furthermore, 124,000 to 172,000WY of exposure would be sufficient to also exclude a twofold risk for ATE (cf. Table 4), assuming that 1) the incidence for DRSP/EE+ is comparable to the EURAS-OC results (~ 1/10,000) and 2) DRSP/EE+ accounts for at least 8% of the total exposure.

Table 4: Power calculation³² for ATE based on the assumption that the true incidence in the DRSP/EE+ cohort is ~ 1/10,000 compared to ~ 2/10,000 in the reference cohort.

Test significance level, α (one-sided)	0.025 (= 0.05 two-sided)	
ATE Incidence for reference cohort	2/10,000 WY	
Non-inferiority margin	2/10,000 WY (equal to twice the ATE incidence for the reference cohort)	
Expected ATE incidence for DRSP/EE+ cohort	1/10,000 WY	
Power (%)	90	
Proportion of DRSP/EE+ users (% of study population)	8	12
Required women years in DRSP/EE+ cohort	13,704	14,858
Required women years in reference cohort	157,594	108,953
Total women years	171,298	123,811

Evaluation Part II

For the primary outcome of interest (VTE/ATE), 90% power is taken as a basis. For the additional outcome of interest (colorectal cancer), a power reduction to 80% is also acceptable.

Power calculations for colorectal cancer are based on an incidence rate of 0.65/10,000WY. As a potential risk for colorectal cancer is associated with folate and not progestogen/estrogen combinations, the assessment of colorectal cancer will be based primarily on the combined COC+ cohort. For this cohort a proportion of 25-35% of the total study population is expected (see above). Based on a proportion of 35% and 25% approx. 531,000 and 644,000 WY of observation, respectively, are needed to exclude a two-fold risk of colorectal cancer (cf. Table 5). i.e., if the proportion should be 25%, it might be necessary to extend the follow-up period by one year as proposed in Table 1b. The final decision on the timely line of the INAS-FOCUS study should be made by the Safety Monitoring and Advisory Council after analysis of the incidence data within this study and discussion of the appropriate measures.

Table 5: Power calculation^{32 33} for colorectal cancer based on the assumption that the true incidence in the COC+ cohort is not different from the reference cohort.

Test significance level, α (one-sided)	0.025 (= 0.05 two-sided)	
Colorectal cancer incidence for reference cohort	0.65/10,000WY	

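### The one-of-three case rule is called the most conservative approach, which holds for absolute incidence but not for the primary test that the VTE hazard ratio is below 2

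*Protocol*

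**What the plan says.** Section 11 makes VTE the primary variable. The null hypothesis is a hazard ratio of 2 or more for DRSP/EE+ against established OCs, and the decision rests on the "comparison of the upper confidence limit for the point estimate of the VTE hazard ratio with the predefined non-inferiority limit". Section 12 sets one-sided alpha at 0.025.

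Section 8 sends reported events to blinded boards; the cardiovascular board has three specialists. The case rule there is: "If at least one adjudicator classifies a report as confirmed VTE or colorectal cancer, the reported event will be considered" confirmed. Appendix 2 repeats the rule as strategy III and gives one reason for it: "The final analysis will be based on strategy III (worst case decision without discussion of split decisions) because it represents the most conservative approach". Strategies I and II (majority vote before and after discussion) are defined, but any analysis other than strategy III is run only if the Safety Monitoring and Advisory Council (SMAC) or a regulator asks for it.

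Two other statements bear on the point. Section 11 bases the safety conclusions on the as-treated analysis, because intention-to-treat may dilute differences between treatments. Appendix 1 says of the investigators' own classification: "Definite and probable events will be classified as 'confirmed events". Its probable category admits clinical diagnoses supported only by tests of low specificity.

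**The concern.** In a non-inferiority test, a conservative choice is one that makes the claim harder to reach. Of the two pre-discussion rules, one-of-three can never be more specific than majority vote: every report that a majority confirms is also confirmed by one vote, and some further reports are too. If some of those further reports are not VTE, and they arise at a similar rate per WY in both cohorts, they add the same amount to the numerator and the denominator of the rate ratio. A true ratio above 1 then shrinks towards 1. At the boundary of 2, where the type I error is defined, this makes a false non-inferiority claim more likely.

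This is the dilution for which section 11 prefers as-treated to intention-to-treat, so the protocol guards against it in one place and describes it as caution in another. What is at stake is the error rate of the main safety conclusion. The protocol itself guarantees no majority-vote check on it.

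**Working it through.** **1. The plan's own figure.** Inputs from section 12, Table 3: rate 9/10,000 WY in both cohorts, margin 9/10,000 WY, one-sided alpha 0.025, power 90%. With k = exposed/reference WY, the exposed WY needed are (1.960 + 1.2816)² × p(1 − p)(1 + k)/Δ².

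- 7% share: 12,542.4 exposed and 166,634.4 reference WY (stated 12,543 and 166,635).
- 12% share: 13,255.0 and 97,203.4 WY (stated 13,256 and 97,204).

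Table 3 therefore reproduces, on a rate-difference scale. On that scale equal false positives cancel: type I error stays at 0.025 and only power falls (0.90 to 0.84 with 0.2 false positives per true case). The stated hypothesis, however, is on the hazard ratio.

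**2. Attenuation of the hazard ratio.** *Assumption:* a share f of counted reference events is false, with the same false-positive rate per WY in both cohorts. The documents give no value for f. Observed HR = (1 − f) × true HR + f. With true HR = 2:

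- f = 10%: 0.9 × 2 + 0.1 = 1.9
- f = 20%: 0.8 × 2 + 0.2 = 1.8
- f = 30%: 0.7 × 2 + 0.3 = 1.7

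**3. Probability of a false non-inferiority claim.** Inputs from section 12: about 185,000 WY of exposure at 5 years, individual products at 7–12% of the total, and incidence "9/10,000WY for VTE and ~2/10,000WY for ATE", so 9/10,000 WY is the counted reference rate.

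At a 12% share there are 22,200 exposed and 162,800 reference WY. Expected reference events are 162,800 × 0.0009 = 146.5. Expected exposed events are 22,200 × 0.0018 = 40.0 at f = 0, and 22,200 × 0.0009 × 1.8 = 36.0 at f = 20%.

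Hand check at f = 20%: SE of the log ratio = √(1/36.0 + 1/146.5) = 0.186. The error is about Φ((ln 2 − ln 1.8)/0.186 − 1.96) = Φ(−1.39) = 8.2%. Exact enumeration over Poisson counts, with a Wald 95% limit for the crude rate ratio standing in for the Cox model, gives 7.1%. The enumerated results are:

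| f | Observed HR | Error, 7% share | Error, 12% share |
|---|---|---|---|
| 0 | 2.0 | 1.9% | 2.1% |
| 10% | 1.9 | 3.1% | 4.0% |
| 20% | 1.8 | 5.0% | 7.1% |
| 30% | 1.7 | 7.9% | 11.9% |

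**4. Unequal false positives.** If the false-positive rate among DRSP/EE+ users is m times the reference rate, observed HR = (1 − f) × 2 + m × f. At a 12% share with m = 1.5 the errors are 2.9, 4.0 and 5.3% for f = 10, 20 and 30%. At m = 2 the observed HR is 2 and the bias is gone. Above 2 the HR is inflated.

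**5. The two voting rules compared.** In step 3, f = 0 means perfect classification, not strategy I. For a direct illustration, assume three independent adjudicators, each with specificity 0.95 and sensitivity 0.85–0.95, and two non-case reports per true case. A non-case is confirmed with probability 1 − 0.95³ = 14.3% under one-of-three, and 3 × 0.05² × 0.95 + 0.05³ = 0.7% under majority vote. By normal approximation (nominal error 0.025):

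- majority vote: observed HR 1.99, error about 0.027;
- one-of-three: observed HR 1.78, error 0.081 (Table 3 size, 7% share) to 0.106 (185,000 WY, 12% share).

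With specificity 0.98, one-of-three gives HR 1.89 and error 0.043–0.050. With specificity 1.00, both rules give HR 2.00 and error 0.025.

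**The case against.** The strongest reply is that the direction is conditional. A reader might infer that blinding makes false positives equal across cohorts. The documents do not support that: section 8 blinds the adjudicators, while the women and their physicians know the product, and section 1 describes an open dispute about VTE with DRSP. More testing or reporting among DRSP/EE+ users would weaken the attenuation or, beyond twice the reference rate, reverse it. This stands, and step 4 shows its effect.

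The extra cases may also be real. Sections 3 and 8 say that diagnoses are not always confirmed by imaging or another highly specific method, so a report accepted by one specialist may be a true VTE. The hazard ratio is then unbiased. The added events narrow the interval, but narrowing alone does not raise the error at a true ratio of 2. This stands too. Section 8's remark on misclassification concerns lay reports before validation, so it cannot supply a value for f.

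A reader might go further and conclude that strategy III must give way to majority vote as the primary definition for VTE, ATE and colorectal cancer. The documents do not carry that. Section 2 includes absolute risk in the primary objective, for which strategy III is cautious; the one-vote sentence in section 8 names VTE and colorectal cancer, not ATE; and histology is the definite standard for cancer in Appendix 1. Nor should the size be read from the combined COC+ cohort, whose larger share would give higher figures: that cohort is a secondary objective.

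Finally, the votes are recorded, and a separate analysis plan, not seen here, may hold sensitivity analyses. That lowers the cost of a remedy. It does not correct the reason stated in Appendix 2.

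**Conclusion.** The point holds in a limited form. The reason given for strategy III is right for absolute incidence and wrong for the primary hazard-ratio test. It also sits badly with section 11's own argument about dilution.

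The size cannot be derived from the documents. The ranges in step 3, up to 7.9% at a 7% share and 11.9% at a 12% share, rest on assumed f values of 10–30%, equal false-positive rates and a crude rate ratio. They compare with perfect classification; the contrast with majority vote in step 5 rests on assumed adjudicator accuracy and independence. The inflation is smaller if false positives are moderately more frequent among DRSP/EE+ users, and absent if the single-vote cases are true events. The documents therefore show a misdirected rationale and an unguarded risk. They do not show that the trial will make a false claim.

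**What to change.** - In Appendix 2, limit the description of strategy III as most conservative to absolute incidence, and align section 8.
- Pre-specify the strategy I (majority vote before discussion) hazard-ratio analysis for VTE beside strategy III, in place of leaving it to a request. Require the upper limit to be below 2 in both before non-inferiority is concluded.
- Add a sensitivity analysis restricted to definite events as defined in Appendix 1.

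No new data are needed, because the individual votes before discussion are already documented. The cost is slightly fewer events in the majority-vote analysis, hence slightly wider intervals, and somewhat lower power for the joint requirement. That loss should be set against section 12's target: "For the primary outcome of interest (VTE/ATE), 90% power is taken as a basis".
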